**Study Product:** **Ferric Carboxymaltose (Injectafer) marketed by American Regent Inc. (Shirley NY)**

**Protocol Number:** **s17-00444**

**IND Number:** **IND Exemption Letter Requested**

## Study Summary

Title	Ferric Carboxymaltose To Improve Skeletal Muscle Metabolism in Heart Failure Patients with Functional Iron Deficiency
Short Title	FCM To Improve Sk. Muscle Metabolism in HF Patients with Fe Def.
Protocol Number	NYULMC IRB number: s17-00444
Phase	Phase 2 study of FDA-approved drug
Methodology	Double-blind, placebo-controlled single center randomized clinical trial
Study Duration	2 years
Study Center(s)	Single Center (NYULMC)
Objectives	To compare the effects of ferric carboxymaltose vs. placebo on skeletal muscle mitochondrial oxidative capacity, submaximal exercise tolerance, and health-related quality of life in HF patients with functional iron deficiency.
Number of Subjects	50 subjects will enrolled to identify 32 subjects eligible for randomization
Diagnosis and Main Inclusion Criteria	Clinically stable ambulatory chronic heart failure patients with functional iron deficiency without contraindication to study procedures (MRI and intravenous infusion of ferric carboxymaltose)
Study Product, Dose, Route, Regimen	Ferric carboxymaltose (Injectafer®) 750 mg intravenously, or normal saline (placebo)
Duration of administration	A single dose of ferric carboxymaltose or placebo will be administered.
Reference therapy	Placebo
Statistical Methodology	The change in the primary and secondary endpoints from baseline to week 4 will be compared between the two treatment arms by two-sided two sample t-test or Wilcoxon rank sum test. Significance will be decided at alpha=0.05.

[figure not shown]

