**Study drug administration:** Intravenous ferric carboxymaltose 750 mg will be mixed under sterile conditions in 100 ml of normal saline for final concentration of 7.5 mg/ml and administered via volumetric infusion pump over 15 minutes. Placebo will consist of 100 ml of normal saline solution, and administered via volumetric infusion pump over 15 minutes. The research pharmacy will dispense study agent based on the randomized treatment allocation sequence.

**Study Agent blinding procedure.** Since ferric carboxymaltose is a dark brown solution, the study agent will be administered by un-blinded research nursing personnel of the NYU Clinical Translational Science Institute who are not otherwise involved in the research study procedures. A licensed physician safety monitor not otherwise involved in study procedures will be available to monitor the infusion procedure. Blinded research personnel will not be present during the study agent infusion. Opaque covers over the study agent infusion equipment and curtains will be used to maintain blinding for the study participants.

**Study Drug Randomization Procedure:** A variable size blocked randomization allocation scheme will be generated by an independent biostatistician and held by the NYU research pharmacy. When an eligible subject arrives at the research site for participation in study visit 2, a study drug order will be placed in the electronic medical record, and a randomization form will be hand-delivered to the NYU Investigational Pharmacy. The Investigational Pharmacist will confirm subject eligibility and assign the treatment allocation based on the sequence of the randomization code. The Investigational Pharmacist will process the study agent order in the electronic medical record, dispense assigned study drug to the un-blinded CTSI research nurse. Case report forms to track the treatment allocation for each participant (ID number and randomization code number) will be

[figure not shown]

Figure 2. Study design overview. FCM=ferric carboxymaltose

completed by the NYU investigational pharmacist, and verified by the unblinded CTSI research nurse assigned to administer study drug. Blinded research personnel will not have access to the randomization case report form. Except in case of emergency, treatment allocation will not be revealed to the investigation team until the last enrolled subject has completed all of the study procedures and the database is locked.

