#### *Adverse Event Definitions*

An Adverse Event (AE) is any untoward medical occurrence in a clinical investigation subject administered a pharmaceutical product and does not necessarily require a causal relationship with the study treatment. An AE can therefore be any unfavorable and unintended sign (e.g., an abnormal laboratory finding), symptom, or disease temporarily associated with the use of a medicinal product, whether or not related to the study procedures. Diseases, signs, symptoms, or laboratory abnormalities already existing at the time of enrollment are not considered AEs unless they worsen (i.e., increase in intensity or frequency). Surgical procedures themselves are not adverse events; they are therapeutic measures for conditions that require surgery. The condition for which the surgery is required may be an AE. Surgical procedures planned prior to randomization and the conditions leading to these measures are not AEs unless the event exacerbates or worsens after randomization.

A Serious Adverse Event (SAE) is any untoward event that:

1. Is fatal
2. Is life-threatening
3. Results in persistent or significant disability or incapacity
4. Is a congenital abnormality or birth defect
5. Requires inpatient hospitalization or prolongation of existing hospitalization with the following exceptions:
  - Preplanned (prior to the study) hospital admissions unless the hospitalization is prolonged.
  - Planned admissions (as part of a study—e.g., routine biopsies)
  - 23 hour hospitalization or re-hospitalizations
  - Hospitalization for elective procedure (e.g. generator change for ICD or pacemaker)
  - Emergency department visits

Important medical events that may not result in death, be life-threatening, or require inpatient hospitalization may be considered an SAE when, based on appropriate medical judgment, they may jeopardize the patient and may require medical or surgical intervention to prevent one of the outcomes listed above.

**Life-threatening** indicates that the patient was, in the view of the investigator, at immediate risk of death from the adverse event as it occurred. It does not include an adverse event that, had it occurred in a more severe form, might have caused death.

**Persistent or significant disability/incapacity** indicates that the event resulted in permanent or significant and substantial disruption of the patients' ability to carry out normal life functions.

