#### **Classification of Adverse Events**

The Principal Investigator will assess all AEs to determine the severity of the event, the possible causal relationship with study drug or study procedures, and whether the event is anticipated or unanticipated according to the following definitions:

1) **Severity.** The severity (intensity) of each AE will be determined by the Principle Investigator according to the following definitions:

**Mild:** Symptom(s) or sign(s) barely noticeable to the subject or does not make the subject uncomfortable. The AE does not influence performance or functioning. Treatments are not ordinarily needed for relief of symptom(s).

**Moderate:** Symptom(s) or sign(s) that cause the subject to be uncomfortable or may require downtitration of study drug. Treatment of symptom(s) may be needed.

**Severe:** Symptom(s) or sign(s) that cause the subject severe discomfort or may cause cessation of treatment with study drug. Treatment for symptom(s) are often needed.

**Life-threatening:** Symptom(s) or sign(s) of a sufficient severity/intensity to cause the subject to be at immediate risk of death. These cases will be classified as a Serious Adverse Event.

2) **Relationship to study procedures.** The temporal/causal relationship between the study procedures and the AE will be determined by the Principle Investigator according to the following definitions:

**Definite:** Clearly related to the study procedures.

**Probable:** Likely (high suspicion) related to the study procedures.

**Possible:** Possibly but not likely (low suspicion) related to the study procedures.

**Unrelated:** Clearly not related to the study procedures.

3) **Anticipated or unanticipated.** The relationship of the AE to the known side effect profile of the study drug and the known clinical manifestations of heart failure and other pre-existing co-morbid conditions will be determined by the Principal Investigator according to the following definitions:

**Anticipated:** Consistent with the known side effect profile of study drug or other study procedures and/or known clinical manifestations of heart failure or other pre-existing co-morbid conditions.

**Unanticipated:** Not known to be associated with study drug, other study procedures, heart failure, or other pre-existing co-morbid conditions.

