#### **IRB Reporting**

Federal regulations require timely reporting by investigators to their local IRB of unanticipated problems posing risks to subjects or others. The following describes the NYULMC IRB reporting requirements, though Investigators at participating sites are responsible for meeting the specific requirements of their IRB of record.

Report Promptly, but no later than 5 working days:

Researchers are required to submit reports of the following problems promptly but no later than 5 working days from the time the investigator becomes aware of the event:

- *Unanticipated problems including adverse events* that are unexpected and related

- Unexpected: An event is “unexpected” when its specificity and severity are not accurately reflected in the protocol-related documents, such as the IRB-approved research protocol, any applicable investigator brochure, and the current IRB-approved informed consent document and other relevant sources of information, such as product labeling and package inserts.
- Related to the research procedures: An event is related to the research procedures if in the opinion of the principal investigator, the event was more likely than not to be caused by the research procedures.
- Harmful: either caused harm to subjects or others, or placed them at increased risk

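### The causality categories and the IRB definition of related name procedures but not study drug, and one SAE exception can be read to exempt any re-hospitalisation

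*Combined protocol and SAP*

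**What the plan says.** **Causality.** The lead-in to Classification of Adverse Events requires the investigator to assess "the possible causal relationship with study drug or study procedures". Item 2, which supplies the scale, is narrower: "The temporal/causal relationship between the study procedures and the AE will be determined by the Principle Investigator". Its title and its four categories (definite, probable, possible, unrelated) refer to study procedures alone. IRB Reporting sets the 5-working-day rule with a matching definition: "Related to the research procedures: An event is related to the research procedures if in the opinion of the principal investigator" judges it more likely than not that those procedures caused it.

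**Seriousness.** In Adverse Event Definitions, the hospitalisation criterion (number 5) carries a list of exceptions. One is "23 hour hospitalization or re-hospitalizations"; another is emergency department visits. A further clause allows, but does not require, other important medical events to be treated as serious on judgment.

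**Severity.** A Moderate event is one that causes discomfort or "may require downtitration of study drug". A Severe event is one that causes severe discomfort or "may cause cessation of treatment with study drug".

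**Dosing.** The Study Summary states: "A single dose of ferric carboxymaltose or placebo will be administered". Under Study Design it is "administered via volumetric infusion pump over 15 minutes".

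**The concern.** Protections Against Risk says the study exceeds minimal risk mainly because of possible side effects of ferric carboxymaltose. Attribution to the drug is therefore the rating a safety reader most needs, and the form implied by the text does not yield it as a separate item.

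Visit 2 makes this practical. The baseline walk test, the MRI with plantar flexion exercise, the intravenous line and the infusion all belong to that visit, so an event on that day has several candidate causes.

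The hospitalisation exception bears on a different count. If re-hospitalisations are exempt as such, an unplanned inpatient stay after dosing may not be classed as serious, in a heart failure population where repeat admission is a familiar event.

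One role, the Principal Investigator, is medical monitor and also judges severity, causality and whether an event was anticipated. Unclear definitions are therefore not corrected by a second assessor.

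**Working it through.** There is no figure in the plan to reproduce. The check sets the sections side by side.

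**1. What causality is judged against**

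| Place | Object of the judgment |
|---|---|
| Classification, lead-in | study drug or study procedures |
| Classification, item 2 title and categories | study procedures only (4 of 4 categories; 0 of 4 name the drug) |
| Classification, item 3 (anticipated or not) | groups the drug with other study procedures, as though it were one of them |
| IRB Reporting, definition of related | research procedures only |
| Potential Risks | introduced as risks of research procedures; the drug is listed first |

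Two readings are possible.

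- *Procedures excludes the drug.* Then the lead-in asks for a drug judgment for which item 2 gives no categories.
- *Procedures includes the drug.* Then there is one rating for infusion, MRI, exercise and phlebotomy together.

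On either reading the record contains no drug-specific attribution.

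**2. What the hospitalisation exception covers**

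The phrase has two grammatical readings.

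- *23 hour limits both nouns.* Only short stays are exempt, and a longer readmission still meets criterion 5.
- *23 hour limits only the first noun.* Any re-hospitalisation is exempt, whatever its length.

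The document does not define re-hospitalisation or the index admission it is counted from. The exceptions attach to criterion 5 only. Fatal, life-threatening, disabling and congenital events remain serious on both readings. For other events on the second reading, the only route back to SAE status is the discretionary clause.

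**3. Whether IRB reporting fills the gap**

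The 5-day rule does not depend on SAE status, which helps. It does require the event to be unexpected. Potential Risks already names anaphylactic and anaphylactoid reactions, so one of these could be judged expected, and Classification counts known manifestations of heart failure as anticipated. The IRB route may therefore not pick up these two kinds of event.

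**4. Severity wording against a single infusion**

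- Down-titration appears in 1 of 4 grades. With one dose there is no later dose to reduce, so the phrase can never apply.
- Cessation appears in 1 of 4 grades. It can apply only within the 15-minute infusion. Because it is joined by *or*, a reaction of low intensity that stops the infusion meets the Severe definition.
- The symptom, functioning and treatment-need criteria stand without these phrases.

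**The case against.** The strongest reply is that the protocol uses procedures as an umbrella term. Item 3 of the classification and the opening of Potential Risks both support this, and the lead-in names the drug outright. A reader might infer that drug causality is undefined; the documents do not support going that far. What survives is that the umbrella reading leaves one pooled rating.

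A second reply is that randomisation does the separating, since placebo patients undergo the same scans, exercise and blood draws. That is right for group comparisons. A reader might infer that safety cannot be tabulated by arm; it can, because a safety analysis set is defined and no causality rating is needed. What cannot be produced is a list of events attributed to the drug.

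Other stronger readings also fail.

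- *Drug reactions will be missed.* Adverse Event Monitoring prompts for new problems at each visit, and the heart failure symptom review collects emergency visits and hospitalisations. The events are captured; the question is how they are classified.
- *A second heart failure admission is exempt.* That is one of two readings, not a stated rule. Because heart failure admissions or emergency visits in the previous 3 months exclude a patient, a second such admission within 4 weeks would usually follow a first post-dose admission that counted, unless another exception applied.
- *The emergency-visit exception removes much.* A visit without admission is not an inpatient stay, so it removes little from criterion 5.
- *Severity is anchored on dose changes that cannot occur.* Down-titration is one alternative in one grade, and cessation can occur during the infusion.

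**Conclusion.** The point holds as a defect of classification, not of capture. The causality defect is the firmest part: none of the four categories and no part of the IRB definition of related names the drug, and this matters whichever way procedures is read. The possible undercount of SAEs depends on the wider reading of the re-hospitalisation exception, which the text permits but does not require. The severity wording is minor.

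No misclassification rate can be derived from the documents. For scale only, one event is 1/16 = 6.25% of the active arm if 32 patients are randomised (Study Summary), or 1/18 = 5.6% if 36 are (Study population). Neither figure estimates how often an event would be misclassified.

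**What to change.** 1. **Causality.** In Classification of Adverse Events, record two ratings for each event, one for study drug and one for study procedures, each on the existing four categories. Name study drug in the definition of related under IRB Reporting.
2. **Seriousness.** Reword the 23-hour exception so that inpatient re-hospitalisations are not exempt as such, and make clear what the 23-hour limit applies to. Keep seriousness independent of causality: making an exception depend on whether an event is rated unrelated to the drug would mix two judgments that the protocol keeps apart.
3. **Severity.** Remove the down-titration and cessation wording so that grading rests on the symptom, functioning and treatment criteria already there. Record infusion interrupted or stopped as a separate field. This changes what is recorded, not how an infusion is managed.

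The cost is text edits, two added adverse event form fields (the second causality rating and infusion interruption), and possibly a few more events classed as serious.

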#### **IRB Reporting**

Federal regulations require timely reporting by investigators to their local IRB of unanticipated problems posing risks to subjects or others. The following describes the NYULMC IRB reporting requirements, though Investigators at participating sites are responsible for meeting the specific requirements of their IRB of record.

Report Promptly, but no later than 5 working days:

Researchers are required to submit reports of the following problems promptly but no later than 5 working days from the time the investigator becomes aware of the event:

- *Unanticipated problems including adverse events* that are unexpected and related

- Unexpected: An event is “unexpected” when its specificity and severity are not accurately reflected in the protocol-related documents, such as the IRB-approved research protocol, any applicable investigator brochure, and the current IRB-approved informed consent document and other relevant sources of information, such as product labeling and package inserts.
- Related to the research procedures: An event is related to the research procedures if in the opinion of the principal investigator, the event was more likely than not to be caused by the research procedures.
- Harmful: either caused harm to subjects or others, or placed them at increased risk

#### Other Reportable events:

The following events also require prompt reporting to the IRB, though no later than 5 working days:

- Complaint of a research subject when the complaint indicates unexpected risks or the complaint cannot be resolved by the research team.
- Protocol deviations or violations (includes intentional and accidental/unintentional deviations from the IRB approved protocol) for any of the following situations:
  - one or more participants were placed at increased risk of harm
  - the event has the potential to occur again
  - the deviation was necessary to protect a subject from immediate harm
- Breach of confidentiality
- Incarceration of a participant when the research was not previously approved under Subpart C and the investigator believes it is in the best interest of the subject to remain on the study.
- New Information indicating a change to the risks or potential benefits of the research, in terms of severity or frequency. (e.g. analysis indicates lower-than-expected response rate or a more severe or frequent side effect; Other research finds arm of study has no therapeutic value; FDA labeling change or withdrawal from market)

#### Other Reportable events:

- **Deviations from the study protocol**

Deviations from the protocol must receive IRB approval before they are initiated. Any protocol deviations initiated without IRB approval that may affect the scientific soundness of the study, or affect the rights, safety, or welfare of study subjects, must be reported to the IRB as soon as a possible, but **no later than 5 working days** of the protocol deviation.

- **Withdrawal of IRB approval**

An investigator shall report to the American Regent Inc. (funding entity) a withdrawal of approval by the investigator's reviewing IRB as soon as a possible, but **no later than 5 working days** of the IRB notification of withdrawal of approval.

## Data Handling and Record Keeping

**Confidentiality:** A random Study ID code will be assigned to each participant. This code will be used on all written and electronic research records. The Principal Investigator and study coordinator will be able to link the Study ID code back to the personal information during the interval of active participation in the study, but this link will be destroyed after the subject has completed the study procedures. Consent forms, links between Study ID and personal information, case report forms, laboratory reports, and results of the 6 minute walking test, and the 31P-MRS and MRI analysis of skeletal muscle bioenergetics in response to plantar flexion exercise will be kept in a project notebook in a locked cabinet in a locked office. Research data without identifiers will be maintained

on the NYULMC REDCap system. The REDCap system provides secure password protected storage of research information behind the NYU firewall and provides quality control and audit trail functions to validate the integrity and quality of the research data.

**Confidentiality and HIPAA:** Information about study subjects will be kept confidential and managed according to the requirements of the Health Insurance Portability and Accountability Act of 1996 (HIPAA). Those regulations require a signed subject authorization informing the subject of the following:

- What protected health information (PHI) will be collected from subjects in this study
- Who will have access to that information and why
- Who will use or disclose that information
- The rights of a research subject to revoke their authorization for use of their PHI.

In the event that a subject revokes authorization to collect or use PHI, the investigator, by regulation, retains the ability to use all information collected prior to the revocation of subject authorization. For subjects that have revoked authorization to collect or use PHI, attempts should be made to obtain permission to collect at least vital status (i.e. that the subject is alive) at the end of their scheduled study period.

**Source Documents:** Source data for the current proposal will include nursing records from the CTSI, case report forms, laboratory reports, and MRI reports. These data will be kept in a project notebook in a locked cabinet in a locked room.

**Case Report Forms:** The study case report form (CRF) is the primary data collection instrument for the study. All data requested on the CRF must be recorded. The data on paper CRF will be transferred to the electronic database and then will be destroyed. The electronic database has quality features to ensure that all fields have entered values, and that entered values are of the correct data entry type, and that numbers fall within pre-specified ranges.

**Records Retention:** Source documents will be retained for at least 2 years after completion of the study. Electronic data will be retained for at least 5 years.

